All Veterans enrolled in the study will be beginning a course of either Prolonged Exposure (PE) or Cognitive Processing Therapy (CPT), which will be delivered as usual by PTSD clinical staff. As the BFI is an adjunctive intervention, Veterans' trauma-focused treatment is considered separate from the present study. The Veterans will be seen by regular clinical staff and no artificial limits will be imposed upon their treatment, although treatment engagement will be tracked (see Assessment section, below). Veterans and their family members will be recruited for the present study at the beginning of a course of treatment at the clinic. Phase I will be an open pilot trial of 4 dyads. All family members in Phase I will receive the BFI, which will be delivered as 2 weekly 50-minute sessions of the BFI, consistent with the application with the BFI in previous work (Thompson-Hollands et al., 2015). Phase II will include 20 dyads (N=40) using identical recruitment, inclusion/exclusion criteria, and assessment structure; however, in this second phase family members will be randomly assigned to receive or not receive the BFI, and VABHS clinicians will deliver the BFI sessions (rather than the PI as in Phase I).

Veterans:

Inclusion criteria.

- (1) has a current diagnosis of PTSD

(2) is 18 years of age or older

(3) has an eligible family member (defined as a spouse/significant other, parent, adult child, sibling, etc., 18 years of age or older who currently has substantial daily or weekly contact with the Veteran)

(4) is beginning a course of either CPT or PE at VA Boston.

Exclusion criteria.

(1) has current diagnoses of unstable bipolar disorder, past or present psychosis, or organic mental disorder

(2) has clear and current suicidal risk (assessed via the MINI-Suicide Module (Sheehan et al., 1998), see Assessment section below)

(3) has current moderate or severe substance use disorder

(4) is currently participating in family-based therapy/couples-counseling

Family members:

Inclusion criteria.

(1) is 18 years of age or older

(2) is the family member (defined as a spouse/significant other, parent, adult child, sibling, etc.) of the Veteran

(3) currently has substantial daily or weekly contact with the Veteran

Exclusion criteria.

(1) has a current diagnosis of PTSD

(2) has current diagnoses of unstable bipolar disorder, past or present psychosis, or organic mental disorder

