During the pilot *Phase I* the PI will serve as the BFI clinician. The PI has considerable clinical experience in the treatment of Veterans with PTSD. Additionally, as described above, the PI designed the BFI and has successfully tested its efficacy in a study of patients with OCD and their family members. Beginning in *Phase II* the PI will no longer deliver the intervention; instead, a minimum of 3 clinicians from the VABHS PTSD clinic will be recruited and trained to deliver the BFI.

Comparison condition: Family members in the control or comparison condition of *Phase II* will not receive the BFI or any other study-specific family sessions (aside from the assessments described below). In keeping with the effectiveness aims of the present study, family members in the comparison condition (and the BFI condition) will not be prohibited from receiving any family-inclusive services or sessions that would normally be offered to them in the context of usual VA care.

Independent variables: Receiving or not receiving the BFI (for Veterans/family members); receiving or not receiving training in the BFI (for clinicians).

Dependent variables: Treatment engagement and PTSD symptoms (for patients); accommodation and active treatment support (for family members); qualitative feedback and rates of participation (for Veterans, family members, and clinicians).

Assessment:

Measures and assessment points are shown in Table 1. Qualitative interviews with stakeholders (Veterans, family members, and clinicians) will continue throughout both Phases of the study, as described below. Clinician-rated assessments of Veterans and family members will be completed (in person or via telephone/mail, or a combination of in person and remotely) at baseline and weeks 6, 12, and 16; Veterans and family members will be compensated \$50 for each of these 4 assessment visits that they complete (total of \$200 for the major assessments). Finally, PE and CPT therapists will complete ratings of Veterans' treatment engagement at each session, and will monitor dropout.

Table 1. Assessment Measures and Timepoints

	Time of Administration					
	Baseline	Weeks 0-6	Every PE/CPT session	Week 6	Week 12	Week 16
CAPS-5	X ^v			X ^v	X ^v	X ^v
SCID-5	X ^{v, f}					
Demographics form (Vet/FM)	X ^{v, f}					
Demographics form (Clin)	X ^{tx}					
Relationship information form (Vet)	X ^v					
Relationship information form (FM)	X ^f					
LEC-5	X ^{v, f}					
WTAR	X ^{v, f}					
MOCA	X ^{v, f}					

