The codes that link the names of participants and their ID numbers will be kept confidential by the PI in a secured cabinet located within the PI's office (JP campus, room 13B-60) (or, during construction on the 13th floor of Building 1 in JP, in a secure basement storage area appropriate for materials containing PII). Collected data forms will be in a locked file cabinet located in the PI's office (or, during construction on the 13th floor of Building 1 in JP, in a secure basement storage area appropriate for materials containing PII). These data are accessible to the PI and personnel working on the project. Data will be entered electronically by trained staff, and data entry discrepancies will be corrected by the data entry supervisor based on source documents. The quality of the data will be monitored quarterly. Data will be securely transmitted using VA approved methods.

Audio recordings will be captured using Philips recorders with FIPS 140-2 validated encryption. Recordings may be obtained while study staff are teleworking; in these cases the recorders will be stored in the home in a locked cabinet/drawer that is only accessible to the study staff member. Recorders will be hand-carried to the VA as soon as it is feasible and safe to do so, at which point the recordings will be uploaded to the PI's personal research drive behind the VA firewall and deleted from the recording device.

The primary outcomes measures will be CAPS-5 total scores and ratings of homework completion (from the Homework Completion Scale), and number of sessions attended/dropout. Data quality will be monitored by inspection of the completed forms by the research assistant and any problems detected will be discussed with the PI. All assessors will be fully trained on the assessment measures, per the usual training procedures within BSD. Adherence to the intervention will be monitored using recordings of sessions and weekly supervision, as described previously. If diagnostic and/or intervention drift is observed, staff will be retrained until acceptable reliability is reached.

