Overview of data analysis: Quantitative data analysis will be performed using MPlus and SPSS, and NVivo management software will be used for qualitative data. Prior to full data analysis, the balance of randomization will be checked and unbalanced factors between groups will be controlled for in subsequent analyses. Similarly, all major variables will be assessed for skewness and outliers, and in cases where parametric analytic assumptions are violated we will use transformations. Preliminary analyses will consist of descriptive statistics by assessment period. All quantitative outcomes will be tested at a two-sided $\alpha=.05$ level.

Data checking: Standard data checking procedures will include checking forms for missing data, double entry with discrepancy resolution, daily back-up copies of computer files, and examination of key variables for skewness, variability, missing data, and outliers. Data will be transformed to achieve normality if needed. If any outcome variable is too zero-inflated to allow for transformation, it will be analyzed with logistic regression or generalized estimating equation techniques (appropriate for this small pilot study).

Missing data: We will make every effort to retain participants, but as treatment engagement is a key outcome of the present study we will also carefully tabulate and report dropout rates and patterns in the present study, including exact timing of dropout. Multilevel regression models will be used to evaluate treatment outcomes; this approach is robust to missing data and is considered "state of the art" for use with unbalanced data sets due to treatment dropout (Schafer & Graham, 2002). There are also several methods for correcting biases due to missing data when using a multilevel regression approach (e.g., pattern-mixture modeling).

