Hypothesis 1 analytic strategy: We will examine the feasibility and acceptability of the BFI by examining rates of BFI recruitment and refusal, as well as level of drop-out from the BFI sessions. These data will be benchmarked to previous BFI efficacy data. We will also assess the success of the clinician training program by reviewing rates of clinician recruitment and attitudes reported on the EBPAS-50. Furthermore, we will conduct detailed in-person, semi-structured exit interviews with Veterans, family members, and clinicians in order to collect qualitative data. These data will allow us to contextualize our findings related to the protocol's fit in this novel setting and its acceptability to Veterans, families, and providers. The qualitative interviews will provide more nuanced feedback regarding the perceived fit of the BFI, and further identify necessary modifications to the protocol (see below for qualitative analytic strategy).

Aim 2: Assess the BFI's effects on symptoms as well as potential mechanisms of change using multilevel modeling.

Hypothesis 2a: Veterans whose family members receive the BFI will show lower levels of PTSD symptoms at post-treatment and greater engagement throughout treatment compared to control Veterans.

Hypothesis 2b: Family members who receive the BFI will show more active support for treatment and less accommodation than control family members.

Hypothesis 2c: Family members' active support for treatment will be positively related to Veterans' treatment engagement, and Veterans' levels of perceived criticism will be negatively related to their treatment engagement

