Hypothesis 2a-2c analytic strategy: Multilevel regression (i.e., hierarchical linear modeling (HLM), growth curve analysis, etc.) will be used to evaluate change in continuous outcome variables (Singer & Willett, 2003). Multilevel regression is a robust method for analyzing change over time, with excellent options for handling missing data, powerful estimation abilities, and flexibility of modeling. This approach will allow for the analysis of an intent-to-treat sample in line with CONSORT guidelines (Altman et al., 2001). For our analysis of change in the variables of interest we will use a multilevel framework in the Mplus program to model time as a Level 1 predictor of the outcome variables (baseline and weeks 6, 12, and 16). We will first specify an unconditional model to ascertain the shape of the change trajectories (e.g., linear versus quadratic change over Time), and will subsequently specify conditional multilevel models to examine treatment effects and the impact of other variables as predictors of individual differences in change. We will also calculate the Cohen's *d* effect size and 95% confidence intervals in order to provide a benchmark for future trials.

o. Literature Cited

Aarons, G. A., Cafri, G., Lugo, L., & Sawitzky, A. (2010). Expanding the domains of attitudes towards evidence-based practice: The Evidence Based Practice Attitude Scale-50. *Administration and Policy in Mental Health and Mental Health Services Research*, 39(5), 331–340. <http://doi.org/10.1007/s10488-010-0302-3>

Boeding, S. E., Paprocki, C. M., Baucom, D. H., Abramowitz, J. S., Wheaton, M. G., Fabricant, L. E., & Fischer, M. S. (2013). Let me check that for you: symptom accommodation in romantic partners of adults with Obsessive-Compulsive Disorder. *Behaviour Research and Therapy*, 51(6), 316–322. <http://doi.org/10.1016/j.brat.2013.03.002>

Borkovec, T.D., & Nau, S.D. (1972). Credibility of analogue therapy rationales. *Journal of Behavior Therapy and Experimental Psychiatry*, 3, 257-260.

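### Covariates are chosen by an undefined balance check after 20 dyads are randomised; prespecify baseline handling for CAPS-5 and SORTS instead, and drop the check as a selector

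*Combined protocol and SAP*

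**What the plan says.** Under Data Analysis, the overview states that "the balance of randomization will be checked and unbalanced factors between groups will be controlled for in subsequent analyses". Neither that section nor any other lists candidate factors, defines imbalance or caps the number of covariates. All quantitative outcomes are to be tested at a two-sided 0.05 level.

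The analytic strategy for Hypotheses 2a-2c will "model time as a Level 1 predictor of the outcome variables (baseline and weeks 6, 12, and 16"), and then fit "conditional multilevel models to examine treatment effects". Baseline is thus the first of four outcome waves. Whether the arms may differ at that wave is not stated. The same section promises Cohen's d and "95% confidence intervals in order to provide a benchmark for future trials". Hypothesis 2a concerns a level: Veterans in the BFI arm "will show lower levels of PTSD symptoms at post-treatment".

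Under Work Proposed, Phase I is an open pilot of 4 dyads and Phase II randomises 20 dyads, half of them to the BFI. Of the measures, "Measures and assessment points are shown in Table 1". CAPS-5 (Veteran) and SORTS (family member) are both taken at baseline and at weeks 6, 12 and 16. The Data Monitoring Plan says "The primary outcomes measures will be CAPS-5 total scores and ratings of homework completion", together with sessions attended and dropout.

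**The concern.** After sound randomisation, a difference between arms at baseline is chance. A rule that adjusts for whatever looks unbalanced therefore selects on the size of a chance difference, not on how strongly a variable predicts outcome. Baseline CAPS-5 is the natural covariate for later CAPS-5, yet the rule brings it in as a covariate only when it happens to look unbalanced. A weak predictor that differs by chance would be brought in. Because the rule has no threshold or list, the adjusted model cannot be written down in advance.

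The multilevel model leaves a second choice open. If arm enters only as a predictor of slope, the baseline means are already common. If arm intercepts are free, the same fit yields two week-16 answers, a difference in level and a difference in change, and a chance baseline gap moves them by different amounts. Hypothesis 2a is worded as a level, while the analytic strategy speaks of change. What is at stake is the reproducibility and precision of the effect size offered to future trials.

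**Working it through.** **Inputs from the documents.** Phase II has 20 dyads, half to the BFI, so n = 10 per arm. The waves are weeks 0, 6, 12 and 16. Alpha is 0.05, two-sided. In Table 1's baseline column, 20 entries are marked for Veterans and 19 for family members. The dyad counts agree (4 + 20 = 24; 2 × 24 = 48). The power sections give no effect size, SD or power, so there is no figure to reproduce.

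**Assumptions (not in the documents).** Baseline to week-16 correlation ρ = 0.3, 0.5 or 0.7. Week-16 SD equal to k = 1, 1.25 or 1.5 times baseline, rising linearly. Compound symmetry or exponential decay. Baseline SD 1, linear time.

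**1. The balance rule, illustrated with a 0.05 t-test.** The documents name no test; this one is assumed.
- The SE of a standardised baseline gap is √(2/10) = 0.447. The test flags a gap above 2.101 × 0.447 = 0.94 SD, which happens in 5% of trials.
- P(|t₁₈| > 0.5/0.447) = 0.28, so gaps of 0.5 to 0.94 SD occur in 0.28 − 0.05 = 23% of trials and are not flagged.
- With one candidate per Veteran instrument, also an assumption, at least one of 20 is flagged in 1 − 0.95²⁰ = 64% of trials if independent. Simulation gives 55% at pairwise correlation 0.3 and 44% at 0.5.

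**2. Effect of a chance baseline gap g = 0.5 SD when arm intercepts are free.** The week-16 mean is expected to move by ρk·g. The change contrast therefore shifts by about (ρk − 1)g and the level contrast by about ρk·g. At ρ = 0.5, k = 1 these are −0.25 and +0.25 SD. Generalised least squares over all four waves gives:

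| k | Shift in change contrast | Shift in level contrast |
|---|---|---|
| 1 | −0.14 to −0.35 | +0.09 to +0.35 |
| 1.5 | −0.30 to +0.03 | +0.14 to +0.53 |

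(Units are baseline SDs.) The change contrast over-corrects in most settings. The exception is ρ = 0.7, k = 1.5, where ρk = 1.05 and the change contrast is almost unaffected. With a common baseline mean the shift is 0.

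**3. Variance of the week-16 effect, known covariance, complete data.** Let s = week/16, X = [1, s], and V be the covariance of the four waves.
- Free intercepts: C = (2/10)(XᵀV⁻¹X)⁻¹. The change contrast is the slope element of C; the level contrast is the sum of all elements of C.
- Common mean: the slope-difference element of the inverse information matrix for a shared intercept, a control slope and a slope difference.

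Hand check at ρ = 0.5, k = 1, exponential decay: change 0.2 × 2(1 − 0.5) = 0.200; level 0.2; common 0.2(1 − 0.25) = 0.150. The four-wave results are 0.200, 0.199 and 0.150. Under compound symmetry they are 0.174, 0.163 and 0.125, a reduction of 1 − 0.125/0.174 = 28% against the change contrast and 1 − 0.125/0.163 = 23% against the level contrast.

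| k | Reduction v change contrast | Reduction v level contrast |
|---|---|---|
| 1 | 15-42% | 5-51% |
| 1.25 | 2-31% | 5-51% |
| 1.5 | 0-22% | 5-51% |

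Entering baseline as a covariate, with weeks 6 to 16 as outcomes and a linear arm effect, costs about 6% more variance than the common mean in every setting.

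**4. Covariance estimated by REML, about 30% missing by week 16.** In one simulation (640 trials per setting, 17 of 18 settings completed, error roughly 3-5 points, not independently repeated), the variance of the change contrast fell by 8 to 34% (k = 1), −3 to 27% (1.25) and −6 to 13% (1.5). A negative value is a loss; the worst was about 6%.

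**5. Precision of d.** The half-width is 2.101√var/k. At ρ = 0.5, moving from the change contrast to the common mean takes it from 0.88-0.94 to 0.74-0.81 (k = 1), and from 0.75-0.81 to 0.72-0.80 (k = 1.5).

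**The case against.** The strongest reply is that the planned model already handles baseline. Because baseline is an outcome wave, a change contrast subtracts any gap, and a slope-only arm term implies common means. A reader might infer from the balance rule that a chance CAPS-5 gap usually goes unadjusted. The documents do not support that: it is wholly true only of a level contrast with free intercepts. This part of the reply stands, and the efficiency gain is conditional on it.

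A reader might also take the 44-64% flag rates, or the 5% and 23% figures, as properties of this plan. They are not. The plan names no test, and speaks of factors without saying that every Table 1 instrument is a candidate.

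Nor should inflated type I error be inferred. In simulation with a single baseline covariate and one follow-up, a fixed 0.05 balance rule rejected a true null in 3.7-4.7% of trials, which is conservative. Error rose to 6.4-8.1% only when the smaller of the adjusted and unadjusted p-values was reported, and nothing in the documents says the investigators would do that.

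Finally, a common mean is justified only if baseline is measured before assignment is known. The consent and baseline measures belong to the first appointment (Work Proposed), while the Human Studies Section has participants told their condition at the start of the first session. The order is not fixed. That text may mean only that participants learn allocation will be random, but the condition must be met, especially for SORTS, which is the family member's own report.

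None of this rescues the balance check as a covariate selector.

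**Conclusion.** The concern holds in a limited form. The covariate rule is undefined and selects on chance, so the model behind the effect-size benchmark is not fixed before data are seen. That does not depend on any assumed correlation.

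The gain from a common baseline mean does. It needs free arm intercepts, which the plan neither states nor excludes, and it rests on assumed correlations and SD ratios. Under known covariance the change-contrast variance falls by 15-42% at equal SDs and 0-22% at an SD ratio of 1.5. With estimated covariance and missing data it may not fall at all. The benchmark stays imprecise either way.

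The gain covers CAPS-5 and SORTS only. Homework ratings, attendance/dropout and the Involvement in Therapy Checklist have no baseline value, although the balance rule touches them too. That Hypothesis 2a names no assessment week is a separate point and is not part of this one.

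The consequence is modest: the study calls itself preliminary and claims no power. The change is worth making because it costs almost nothing.

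**What to change.** Amend the SAP wording as follows.
- Delete the balance check as a covariate selector and report baseline balance descriptively.
- For CAPS-5 and SORTS, in the 20 randomised Phase II dyads only, prespecify a common baseline mean across arms in the four-wave model. Baseline stays an outcome and is not also a covariate. The 4 Phase I dyads stay out of this contrast. Prespecifying baseline as a covariate with weeks 6, 12 and 16 as outcomes is acceptable, at about 6% more variance.
- Name any other covariate, with its reason, before outcome data are seen. This includes the outcomes without a baseline.
- State that baseline measures are completed before assignment is disclosed. If that cannot be assured, do not impose the common mean, above all for SORTS.

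No new data are needed, since both baselines are in Table 1. The statistical cost was nil under known covariance and, in the simulation with estimated covariance and missing data, at worst about 6% more variance.

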(2) has clear and current suicidal risk (assessed via the MINI-Suicide Module (Sheehan et al., 1998), see Assessment section below)

(3) has current moderate or severe substance use disorder

(4) is currently participating in family-based therapy/couples-counseling

Recruitment of Veterans and family members will occur through the VABHS outpatient mental health clinics (e.g., the PTSD Clinic, the Women's Clinic, General Mental Health, Center for Returning Veterans, etc.). All interested participants will be contacted by the PI for a phone screen, where the study and its procedures will be described and a short screen for eligibility will be administered. If the initial screening requirements are met, participants will be invited to an in-person assessment. During the first appointment, the Veteran and family member will be provided with a thorough description of the project and the informed consent form will be reviewed and signed. Baseline assessment measures will then be administered (see Assessment section).

Veterans will proceed with PE or CPT as usual through the clinic, with no restrictions or limitations. Should a Veteran choose to discontinue PE or CPT, he or she will continue to be enrolled in the proposed study for follow-up assessments, as treatment drop-out is a variable of interest. All family members who are to receive the BFI (i.e., all family members in *Phase I* and half of family members in *Phase II*) will participate in the two BFI sessions, and then move into the follow-up portion of the study.

BFI: The BFI is a 2-session individual intervention delivered by a clinician to the adult family member of a Veteran with PTSD who is beginning a course of CPT or PE treatment. The BFI sessions are guided by a manual, which has previously been developed by the PI but will

be revised for the purposes of the current study as described earlier to enhance its relevance to the families of Veterans with PTSD. The BFI may be completed either in person or remotely via telephone.

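### No estimator or small-sample degrees of freedom is named for multilevel models on 10 v 10 dyads; with a normal reference, a random-slope group-by-time test rejects about 5–8% under no effect instead of 5%

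*Combined protocol and SAP*

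**What the plan says.** All references are to the combined protocol and SAP.

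- **Sample.** Section (4), Work Proposed: "Phase II will include 20 dyads (N=40"). The intervention goes to everyone in Phase I and to "half of family members in" Phase II. Each outcome therefore has 20 independent units, 10 v 10.
- **Test level.** DATA ANALYSIS, Overview of data analysis: "All quantitative outcomes will be tested at a two-sided" alpha of .05.
- **Model.** Hypothesis 2a-2c analytic strategy: "we will use a multilevel framework in the Mplus program to model time as a Level 1 predictor of the outcome variables", at baseline and weeks 6, 12 and 16. Conditional models then examine treatment effects and "the impact of other variables as predictors of individual differences in change". That wording points to random slopes, although the random effects are not written out.
- **Software.** "Quantitative data analysis will be performed using MPlus and SPSS".
- **Fallback.** Data checking: "If any outcome variable is too zero-inflated to allow for transformation", logistic regression or "generalized estimating equation techniques (appropriate for this small pilot study") will be used. This is the only remark on small size attached to an analysis method, and it does not concern the multilevel models.
- **Status.** Both power paragraphs call the study preliminary. The one in DATA ANALYSIS adds that sample-size rules for multilevel models are disputed. Neither leads to a small-sample method.

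No section names ML or REML, a t reference, a degrees-of-freedom method, a bootstrap or a permutation test.

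**The concern.** With 20 independent units, the estimator and the reference distribution affect the actual test level. ML understates the between-person variance, and a normal reference ignores that this variance is estimated on only 18 degrees of freedom. Both push the rejection rate up. CAPS-5 total score is a primary outcome (Data Monitoring Plan), and Hypotheses 2a and 2b are to be tested at .05. The results are meant to inform a fully powered study.

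Leaving the choice open also means it could be made after the data are seen. On the scale of an unbiased standard error, the critical value is 2.101 for REML with t(18) and 1.859 for ML with a normal reference, a drop of about 11.5%. That is enough to change a borderline result.

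**Working it through.** The plan gives no power or sample-size figure to reproduce. Its only error-rate figure is the nominal .05, and a t reference on 18 degrees of freedom gives exactly that in the closed form below.

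**Inputs from the documents.** 20 dyads, 10 v 10; four common times (weeks 0, 6, 12, 16); two-sided .05, so z = 1.960.

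**Inputs assumed.** Complete data; random intercept and slope; all variances (the documents give none).

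**Closed form.** With balanced complete data the group-by-time estimate is the difference between the two mean per-person slopes. Its variance is estimated on 20 − 2 = 18 degrees of freedom, provided the estimated slope variance is off its boundary.

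- Unbiased standard error (REML), normal reference: P(|t18| > 1.960) = 6.57%.
- ML, variance divisor 20 in place of 18: 1.960 × √(18/20) = 1.859, and P(|t18| > 1.859) = 7.94%. A sandwich standard error gives the same with complete data.
- Unbiased standard error, t(18): P(|t18| > 2.101) = 5.00%.

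**Simulation under no effect.** The closed form fails when the fit is on the boundary, so it was checked by simulation with time scaled 0–1. The Monte Carlo standard error is about 0.4 points.

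| Assumed variation | ML, z | REML, z | REML, t(18) |
|---|---|---|---|
| Variances (intercept, slope, residual) .5, .49, .25 | 7.0–7.4% | 6.0–6.5% | 4.6–5.1% |
| Variances .5, .15, .35 | 5.6–6.1% | 5.0–5.4% | 3.6–4.0% |
| Intercept SD 1, residual SD 0.6, slope SD 1.2 | 7.8% | 6.5% | 4.7% |
| Same, slope SD 0.8 | 6.9% | 5.8% | 4.4% |
| Same, slope SD 0.4 | 5.8% | 5.2% | 3.9% |
| Same, slope SD 0 | 4.5% | 4.0% | 2.9% |

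The ranges in the first two rows cover three settings of the intercept–slope covariance. The estimate was on the boundary in about 47% of trials at slope SD 0.4 and 67% at slope SD 0, which is why the excess disappears there. A smaller run (1,000 trials per setting, Monte Carlo standard error up to about 0.9 points) gave 6.2–8.3%, 5.4–7.0% and 3.6–5.2% in the same column order.

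**Coverage.** This is 1 minus the rejection rate. With a normal reference it runs from 92.1% (ML closed form) to about 95% (REML, small slope variance).

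**Cost in width.** 2.101/1.960 = 1.072 relative to REML with z. Multiplying by √(20/18) gives 1.130 relative to ML with z.

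**Fallback (secondary; event rates and within-person correlations assumed).**

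- Binary outcome, group-by-time effect: uncorrected GEE with robust z rejects 7.0–9.0%; with the Mancl-DeRouen variance, 4.6–6.6%.
- Binary outcome, group effect averaged over visits: uncorrected 4.7–7.3% (median 6.3%); corrected 2.7–4.6%.
- Logistic Wald test at 36% in both arms (the dropout figure in the Statement of the Problem): 2.7% by exact enumeration. An arm has no events or all events with probability .64^10 + .36^10 = .0116, so there is no finite estimate in 1 − (1 − .0116)² = 2.3% of trials.

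**The case against.** The strongest reply is that the plan never states a normal reference, that the excess is small, and that this is a pilot with no power claim and no decision tied to p < .05. All of that is right and limits the point. A reader might infer that the trial will run uncorrected tests, or that its tests will exceed 5% come what may. The documents support neither: the method is unspecified, SPSS is named alongside Mplus, and with near-zero slope variance the normal-reference test rejects 4.0–4.5%.

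The remedy is also not better everywhere. With small slope variance, REML with z gives 5.0–5.4% and REML with t(18) gives 3.6–4.0%, which is further from 5% and costs some power. That stands. Moreover, the simulations used a fixed t(18), not Satterthwaite or Kenward-Roger degrees of freedom themselves.

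Four other stronger readings do not hold:

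- **Cohen's d interval.** This is what the plan offers as a benchmark for later trials. The plan gives no formula for it, and the usual large-sample interval (variance .2 + d²/40) covers 94.6% at 10 v 10.
- **Loss to follow-up.** If only 16 or 13 people informed the slope, the closed forms would give 7.0–8.8% or 7.6–9.9%. But the 36% in the background is dropout from therapy, and Veterans who stop therapy stay in for assessments, so no assessment loss is documented.
- **A model without random slopes.** Leaving out slope variation that exists would be misspecification and not a small-sample effect, and the plan's wording points the other way.
- **The fallback as a present fault.** It applies only if an outcome proves too zero-inflated, and no outcome is identified as such. For group effects the corrected GEE variance is not clearly nearer 5%.

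What survives is that the plan fixes a level of .05 and a multilevel framework in Mplus for 20 units and names nothing that would hold that level.

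**Conclusion.** The omission is confirmed and its consequence is conditional and modest. With a normal reference in a random-slope model, the departure from 5% is about 0 to 3 points per test: up to 7.9% for ML and 6.6% for an unbiased standard error, and nothing or slightly below 5% when people barely differ in rate of change. These figures rest on complete data, 10 v 10 and assumed variances, so the documents do not settle where in the range the trial falls. The coverage shortfall applies to the model coefficient only. The change is worth making because it is cheap and, on the whole, keeps the test nearer the stated level or on its conservative side.

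**What to change.** In the Overview of data analysis and the Hypothesis 2a-2c analytic strategy, state that multilevel treatment effects will be fitted by REML and tested with Satterthwaite or Kenward-Roger degrees of freedom, for example in SPSS. State that 95% intervals for model effects will come from the same fit.

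As a secondary suggestion, if the zero-inflation fallback is used, prefer a small-sample-corrected GEE variance (for example Mancl-DeRouen), mainly for group-by-time effects, and Firth or exact methods for sparse binary outcomes.

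The cost is SAP wording only; design, recruitment and data collection do not change. Against it:

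- Intervals for model effects are about 7–13% wider.
- The main models may have to move from Mplus to SPSS.
- The test is somewhat conservative, about 3–4% with a t reference on 18 degrees of freedom, if slope variance is small.
- The team must check that its software offers the corrected GEE variance, which is itself somewhat conservative for group effects.
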